8.8 Secondary study parameter(s)

RCT

The main clinical analysis of the study consists of a comparison between the trial treatment groups (DBS versus CLI) of the primary clinical outcome (PDQ-39) 12 months after the start of the study treatment. First, the follow-up difference between PDQ-39 scores will be analysed using a two-group t-test. Second, the PDQ-39 follow-up scores will be further investigated using multiple linear regression taking into account patients' PDQ-39 baseline values, the stratifying variables (experience of the including centre with DBS and CLI; response to Levodopa) and (if necessary) for clinically relevant baseline imbalances. Additionally, the repeated data structure will be investigated with a linear mixed model. The same analyses will be performed for the 24 and 36 month outcomes. With regard to the comparisons of the other secondary outcomes PD motor symptoms (MDS-UPDRS, CDRS, 3-day motor symptom diary), non-motor symptoms such as autonomic functions and sleep (Non Motor Symptom Checklist, Rotterdam Symptom Checklist), PD-medication, neuropsychological and psychiatric assessment, disability, functional health status (ALDS), patient and physician preferences, patient satisfaction, adverse effects and complications, treatment failure, stopping treatment, starting with the alternative than initially started treatment, caregiver burden and medical and non-medical care costs (iMCQ, iPCQ) we will use the appropriate parametric and non-parametric statistics. In all analyses, statistical uncertainties will be expressed in 95% confidence intervals.

Patient preference trial

As mentioned before a patient preference observational study will be conducted to asses external validity of the randomized controlled trial results. The primary clinical outcome of the non-randomized group and randomized group will be compared using the two-group t-test and linear regression, whereas baseline characteristics will be compared with the

Version 7: 23-10-2019 32 of 48

two-group t-test and Chi-square test, when appropriate. Finally, the impact of the treatment on the PDQ-39 follow-up scores of the randomized and non-randomized group will be analysed using multiple linear regression, adjusting for relevant imbalanced baseline variables and randomized status (agreeing to randomization or not).

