This design of the study was an RCT with ancillary patient preference observational arms which is also known as a "patient preference trial" or "comprehensive cohort study".³ In the RCT, patients with PD who met the inclusion criteria and who were willing to be randomized between CLI and DBS treatment were assessed for eligibility for both treatments. Eligible patients were randomized using online computer software (ALEA, Amsterdam UMC). Quality of life, costs, disability, PD specific motor and non-motor symptoms, neuropsychiatric comorbidities and caregiver burden were assessed 12, 24 and 36 months after initiation of advanced therapy (*i.e.*, CLI and DBS). Furthermore, at three, six, and nine months follow-up, additional assessments regarding costs, utilities and adverse events were planned.

It was expected that only a proportion of patients would be willing to be randomized between the two freely available therapies. Patients who were eligible to participate in the RCT but were not willing to be randomized, were asked to participate in the ancillary patient preference observational study. The observational study arms served primarily to determine the extent of the external validity of the RCT-results. Furthermore, data from RCT patients were pooled with data from the patients participating in the ancillary patient preference observational study, to compare specific clinical outcomes in a larger population. We aimed to randomize a total of 66 patients. There was no minimum of participants in the ancillary patient preference observational arms. Although an open-label study, data collection was performed by investigators who had no therapeutic relationship with study participants. Study data was not accessed by treating physicians. Treating physicians were aware of patients' study participation and allocated treatment if appropriate. Patients were treated in accordance with the center specific usual care regarding the procedures (*e.g.*, planning of DBS approach, usage of general anesthetics during placement of the DBS electrodes, possible pre-CLI medication test phase, and dose or device settings).

Synopsis of study protocol development

The first patient was included in December 2014. During the study, new insights and potential weaknesses in the original design were addressed in (substantial) amendments of the study protocol. Major adjustments are presented below. If applicable, this is also addressed in the relevant following paragraphs.

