CLI: continuous intrajejunal levodopa infusion, DBS: deep brain stimulation, RCT: randomized controlled trial, SAE: serious adverse event

Ancillary patient preference observational study arms

For both the observational CLI and DBS groups, changes in outcomes from baseline to 12 months after start of treatment were displayed in Table SAP4. The numbers of patients who stopped their advanced treatment and who switched between advanced treatments were reported.

To assess the extent of external validity of the mITT population, differences in baseline characteristics of all randomized patients (*i.e.*, both the CLI and DBS groups combined) and the separate observational (*i.e.*, non-randomized) CLI group and DBS group of the ancillary patient preference study were shown with 95% CI in supplementary Table SAP1-S. With regard to the main clinical outcome (the change in PDQ-39 summary index scores at 12 months relative to baseline), the difference between patients randomized to CLI treatment (mITT population) and those who preferred that treatment was reported with 95% CI. The same was done for patients randomized to DBS treatment (mITT population) and those who preferred that treatment. These figures were presented in the text.

To assess the impact of the treatment on the change in PDQ-39 at 12 months relative to baseline with more power, this was analyzed using multivariable regression in the total group of patients (*i.e.*, both the mITT randomized population and non-randomized population), taking into account significant imbalanced baseline variables and participation in the RCT or preference observational study.

Table SAP4. Ancillary patient preference observational study arms, outcomes at 12 months.

Outcome	Baseline				Within-treatment Change from Baseline to 12 Months			
	CLI		DBS		CLI		DBS	
	no. of patients	mean±SE	no. of patients	mean±SE	no. of patients	mean±SE or n (%)	no. of patients	mean±SE or n (%)
Main clinical outcome PDQ-39 summary index score								
Secondary outcomes LEDD (mg per day) ALDS score in on-phase								

ALDS: Amsterdam Linear Disability Scale, CLI: continuous intrajejunal levodopa infusion, DBS: deep brain stimulation, LEDD: Levodopa Equivalent Daily Dose, PD-CRS: Parkinson's Disease Cognitive Rating Scale, PDQ-39: Parkinson's Disease Questionnaire-39, SE: standard error. For continuous variables, mean and Standard Error were reported, for dichotomous variables the number of patients (n) and percentage (%).

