Appendix II — Flowchart ancillary patient preference observational study

Appendix III — Supplementary statistical analysis tables

Table SAP1-S. Baseline characteristics – RCT mITT population and ancillary patient preference observational study arms

	RCT all – all randomized patients (CLI or DBS)	Observational CLI – patients chose CLI treatment	Observational DBS – patients chose DBS treatment	Difference RCT all vs observational CLI difference (95% CI)	Difference RCT all vs observational DBS difference (95% CI)
Age (years)	n	n	n		
Sex, F (%)					
Time since PD diagnosis (years)					
Hoehn and Yahr stage in on-drug state (%)					
- Stage 1					
- Stage 1,5					
- Stage 2					
- Stage 2,5					
- Stage 3					
- Stage 4					
Levodopa-equivalent daily dose (mg/day)					
Level of experience of treating center with CLI and DBS treatment (%)*					
- Experienced in CLI, not in DBS					
- Experienced in DBS, not in CLI					
- Experienced in both CLI and DBS					
- Little experience in both CLI and DBS					

CLI: continuous intrajejunal levodopa infusion, DBS: deep brain stimulation, F: female, MDS-UPDRS: Movement Disorder Society's Unified Parkinson's Disease Rating Scale, mg: milligrams, NA: not available, PD: Parkinson's disease, RCT: randomized controlled trial

*Experienced in CLI/DBS: ≥ 5 patients treated per year in the two years previous to including the patient with the respective treatment in the treating center. A center may have changed in level of experience over time.

For normally distributed data, mean and standard deviation were presented, for non-normally distributed data median and interquartile ranges. For dichotomous variables, the percentage stated.

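### The randomised-versus-preference comparison of PDQ-39 change has no baseline-adjusted estimate per therapy, and the regression the protocol planned for it is omitted without explanation

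*SAP*

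**What the plan says.** The SAP's synopsis of the original protocol gives the purpose of the preference arms: "The observational study arms served primarily to determine the extent of the external validity of the RCT-results".

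Protocol 8.8 (Patient preference trial) plans two regressions.

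- **Cohort comparison:** "The primary clinical outcome of the non-randomized group and randomized group will be compared using the two-group t-test and linear regression". No covariates are named.
- **Pooled treatment-effect model:** a multiple regression of follow-up PDQ-39, "adjusting for relevant imbalanced baseline variables and randomized status (agreeing to randomization or not").

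The SAP section on the ancillary preference arms keeps the pooled model, "taking into account significant imbalanced baseline variables and participation in the RCT or preference observational study". Its stated aim is to estimate the treatment effect with more power. For external validity, the SAP states that "the difference between patients randomized to CLI treatment (mITT population) and those who preferred that treatment was reported with 95% CI", and likewise for DBS. It names no model or covariate. The synopsis of protocol development does not mention the omitted regression.

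Baseline data appear in four places.

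- **Table SAP1** shows the mITT arms and the preference arms side by side, without differences and without PDQ-39.
- **Tables SAP2 and SAP4** show baseline PDQ-39 by arm, for the mITT and preference patients respectively.
- **Table SAP1-S** is the only one with cohort differences and confidence intervals. The text introduces it this way: "To assess the extent of external validity of the mITT population, differences in baseline characteristics of all randomized patients", both arms combined. Its title says mITT, its first column is headed "all randomized patients (CLI or DBS"), and it has no PDQ-39 row.

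**The concern.** Patients who accepted randomisation and patients who chose their therapy may differ at the start. Change from baseline usually depends on the starting level, so part of any cohort difference in change may reflect different baseline severity. A baseline gap in one direction could suggest that the trial does not generalise when it does. A gap in the other direction could hide a real difference.

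The plan gives the reader little help in telling these apart. The per-therapy comparison is unadjusted. The only table with baseline differences and intervals pools the two randomised arms, whereas the outcome comparison is by arm. Baseline PDQ-39, the variable most directly tied to PDQ-39 change, is not in that table. The pooled model picks covariates by significant imbalance, so no planned comparison would trigger the inclusion of baseline PDQ-39.

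The pooling matters for CLI in particular. The SAP reports that several patients refused CLI straight after allocation, and its mITT rule removes them. A column of all randomised patients from both arms does not show who remains in the CLI mITT group.

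**Working it through.** **1. Reproducing the protocol's figures (section 4.4).** Inputs: two-sided alpha 0.05, power 80%, SD 15, 33 randomised per arm, and 108 DBS and 72 CLI preference patients (72 and 48 if only 120 take part, at the same 60/40 split). Detectable difference from the two-sample t-test (noncentral t):

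| Comparison | Computed | Stated |
|---|---|---|
| DBS, 33 v 108 | 8.42 | 8.4 |
| DBS, 33 v 72 | 8.92 | 8.9 |
| CLI, 33 v 72 | 8.92 | 8.9 |
| CLI, 33 v 48 | 9.62 | 9.6 |

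All four reproduce. They concern an unadjusted follow-up score and allow for no dropout.

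**2. Effect of a baseline gap on unadjusted change.** Let rho be the correlation between baseline and 12-month PDQ-39. Assume equal SDs at both times, the same regression line in both cohorts, and no true cohort effect. The expected 12-month score is then a + rho × baseline, so the expected change is a + (rho − 1) × baseline. A gap g in mean baseline gives a spurious difference in change of size (1 − rho) × g.

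| Gap g | rho 0.3 | rho 0.5 | rho 0.7 |
|---|---|---|---|
| 5 points | 0.7 × 5 = 3.5 | 0.5 × 5 = 2.5 | 0.3 × 5 = 1.5 |
| 10 points | 0.7 × 10 = 7.0 | 0.5 × 10 = 5.0 | 0.3 × 10 = 3.0 |

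The SAP's minimal clinically important difference is 1.6. Every entry exceeds it except 1.5, which is just below. Both g and rho are assumptions.

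**3. How often this would look like a cohort difference.** For CLI (33 v 72), the SD of change is 15 × √(2(1 − rho)): 17.7, 15.0 and 11.6 at rho 0.3, 0.5 and 0.7. The chance that the 95% interval excludes zero from the gap alone is 9–15% for a 5-point gap and 23–46% for a 10-point gap, against 5% nominal.

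**4. Precision.** With baseline adjustment, the residual SD is 15 × √(1 − rho²). The half-width of the 95% interval for CLI is 1.98 × SD × √(1/33 + 1/72) = 1.98 × SD × 0.2102.

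| | rho 0.3 | rho 0.5 | rho 0.7 |
|---|---|---|---|
| Unadjusted change | 7.4 | 6.2 | 4.8 |
| Baseline-adjusted | 6.0 | 5.4 | 4.5 |

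The adjusted row ignores the small loss from the gap itself. For g = 5 the variance rises by the factor 1 + [25/(103 × 225)]/0.0442 = 1.024, so 5.41 becomes 5.41 × √1.024 = 5.47. The mITT arm will hold fewer than 33 patients if any are excluded, which widens both rows.

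**5. Whether the pooled model fills the gap.** It has one participation term. Without other covariates, least squares weights each therapy by n₁n₂/(n₁ + n₂): CLI 33 × 72/105 = 22.6, DBS 33 × 108/141 = 25.3. If the true cohort differences were +5 in CLI and −5 in DBS, the single term would estimate 5 × (22.6 − 25.3)/(22.6 + 25.3) = −0.3. A simulation with these sizes also gave −0.3. Opposite differences would cancel, so this model cannot replace a per-therapy estimate.

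**The case against.** **The raw difference answers a fair question.** The aim is external validity. If patients who choose their therapy change differently because they start from a different level, that is itself a limit on generalisability. This stands, and it is why the unadjusted estimate should be kept.

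**Adjustment is not assumption-free here.** If each cohort regressed towards its own mean, the change score would be the fairer comparison. This also stands, and it favours showing both estimates.

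**Change scores were chosen to deal with baseline differences.** The synopsis of protocol development argues that change is largely independent of them. A change score removes part of a gap, but under the model above a share of 1 − rho remains.

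**No decision depends on this comparison.** It is ancillary and reported as an interval only, because the SAP gives P-values for no clinical outcome except the main one. That limits the consequences.

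Three stronger readings are tempting but unsupported.

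- A reader might infer that the SAP abandoned the protocol's adjusted analysis. The pooled regression, the one for which the protocol names adjustment, is kept with a participation term. The omitted regression has no stated covariates, so that it would have adjusted for case mix is an inference.
- A reader might infer that the groups are never shown together at baseline, or that baseline PDQ-39 is absent. Tables SAP1, SAP2 and SAP4 show otherwise; what is missing is the by-arm difference with its interval.
- A reader might infer that case mix will be taken for a preference effect. The documents give no gap and no correlation, so they support only that it could be.

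**Conclusion.** The point holds as a gap in an ancillary analysis. The per-therapy cohort comparison is unadjusted, the protocol's linear regression for it is omitted without explanation, and the pooled model does not replace it. The only planned baseline differences with intervals pool the randomised arms, omit PDQ-39, and sit under a title that disagrees with the column head.

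The possible distortion is 1.5 to 3.5 points for a 5-point baseline gap over rho 0.7 to 0.3, around or above the 1.6-point minimal difference. It rests on equal SDs, a common regression line, and an assumed gap and rho. It could act in either direction. The unadjusted difference is incomplete rather than wrong. The primary randomised comparison and the economic analyses are unaffected.

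**What to change.** 1. Keep the unadjusted difference as the descriptive result. Beside it, for each therapy, report a regression of 12-month PDQ-39 (or change) on cohort, mITT-randomised versus preference. Include baseline PDQ-39 and a short prespecified covariate set recorded in both cohorts, for example age, sex, disease duration and LEDD. Because the protocol names no covariates, present this set as a new specification.
2. In the pooled model, always include baseline PDQ-39 and add a treatment-by-participation term.
3. In Table SAP1-S, add a baseline PDQ-39 row and by-arm differences with 95% intervals (CLI mITT versus CLI preference, DBS mITT versus DBS preference). Reconcile the title with the column head. The all-randomised column can stay if labelled as such.
4. List the departure from protocol 8.8, with a reason, in the synopsis of protocol development.

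The cost is some SAP wording, two extra estimates and a revised table. All the variables are already collected.

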4.4 Sample size calculation

RCT

The primary objective of the study is to realize an efficient allocation of resources to the available treatment options in advanced PD. For this, primarily an economic evaluation will be carried out and the sample size has been calculated accordingly. Society's willingness-to-pay (WTP) per Quality Adjusted Life Year (QALY) may be indicative of whether or not CLI is affordable compared to DBS. The Dutch Raad voor de Volksgezondheid (RvZ) reported a value of €80,000 per additional QALY in 2006 as a potential upper limit of affordability. Explicitly, the figure is reported by the RvZ as a potential, but also unofficial limit: it should

Version 7: 23-10-2019 16 of 48

not be taken as a definite one. Other arguments based on patient preference or access to health care should be taken into account as well. Considering that CLI may be a less invasive intervention and access to health care is easier to facilitate when two interventions can be provided, a more lenient upper limit for the extra societal costs per additional QALY may be appropriate here. We propose a sample size calculation based on a WTP per additional QALY of €120,000 (50% above the RvZ figure). Based on the net health benefit formula suggesting that differences in QALYs between the interventions should be larger than the difference in costs (i.e., €34,174 a year) divided by the maximum WTP (i.e., €120,000 per QALY) in order for one intervention to be accepted as more efficient than another intervention, CLI treatment should at least outperform DBS treatment by 0.2847 QALY per year. Based on literature data with comparable costs estimates, [6] we anticipate standard deviations (SD) for QALYs up to 0.35 and for total costs up to €10,000 (factoring in a 12-month follow-up and non-responders).

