To achieve 80% power and given a two-sided significance level of 0.05, up to 26 patients per group (or 52 in total) are needed to detect a difference of at least 0.2847 QALY for WTP-values up to €120,000 and a worst case scenario of zero correlation between costs and clinical effect, using a two-group t-test. Accounting for a possible dropout of 20%, we will randomize 66 patients (33 per group). With this sample size and given the same test conditions (power, type-I error rate, test chosen, drop-out rate) we are also able to detect a difference in mean PDQ-39 scores between both groups of 11.9, assuming an expected mean score of 32 in the DBS group and a standard deviation of 15.

Motivation for standard deviations for QALY

Literature data [8-10] show that the standard deviation for PDQ-39 scores from operated PD patients equals 15 points and that a 4 to 5 points difference is associated with a QALY difference of approximately 0.1,[16] suggesting a standard deviation for QALYs of up to 0.35.

Patient preference trial

We (conservatively) estimate that during the inclusion period a total of 180 patients (60% of the eligible patients) may decline to participate in the RCT, but are willing to take part in the preference observational study. Based on our clinical experience it is expected that 60% of these patients (n=108) prefers DBS, against 40% (n=72) preferring CLI.

When comparing the effect of DBS treatment of patients who express a preference for that treatment with the effect of DBS treatment in the randomised patients, and given the same test conditions (power, type-I error rate, two group t-test) we are able to detect a difference in

Version 7: 23-10-2019 17 of 48

mean PDQ-39 scores between both groups of 8,4, assuming an expected mean score of 32 in the randomized DBS group and a standard deviation of 15.

In case only 120 patients (40% of the eligible patients) agree to take part in the preference observational study, we are able to detect a difference in mean PDQ-39 scores between both DBS groups of 8,9.

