According to the Consolidated Standards of Reporting Trials 2010 statement (CONSORT), a flow diagram illustrating the number of participants ineligible, eligible, consented, randomized, received allocated treatment, excluded, withdrawn and lost to follow-up for the primary outcome was provided. Please see the Figure SAP-1 on page 29.

Analysis populations

Modified intention-to-treat population

The primary analysis consisted of the modified intention-to-treat (mITT) population which included all randomized patients who received the allocated treatment, regardless of continuation of treatment. Analyses in the original ITT population including all randomized patients, regardless of the treatment they had actually received (*i.e.*, also patients not receiving the allocated treatment and patients quitting study participation immediately after randomization) were accounted for in sensitivity analyses (see page 12, “Sensitivity analysis”) and were presented in the supplements.

As-treated population

To provide insight in potential bias resulting from excluding patients who did not adhere to the allocated treatment or switched treatment, analyses were additionally performed in an as-treated population categorizing the randomized patients according to the actual treatment(s) they were receiving at the moment of the 12-month visit (if available).⁷

Per protocol population

The per protocol population consisted of all patients receiving the allocated treatment who completed the study protocol without protocol violations.

Ancillary patient preference population

The ancillary patient preference population consisted of all patients who signed informed consent for this element of the study, started the chosen treatment and underwent at least the baseline visit and one follow-up visit. Patients were allowed to participate in the ancillary patient preference cohort study after withdrawal of consent for the RCT prior to randomization. Please see also Appendix II for the flowchart of the Ancillary patient preference cohort.

Adherence and protocol deviations and violations

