For other clinical outcomes at 12 months, the last observation was carried forward if available from another visit (excluding baseline). For baseline characteristics, missing values were not imputed. For displaying baseline characteristics, the numerator and denominator were stated for dichotomous

variables (e.g., male: 5/15). For continuous variables, the number of patients for whom the variable was available was stated.

Study population

Baseline characteristics

For both the RCT mITT population and for the ancillary patient preference population, baseline characteristics were presented in Table SAP1. Categorical baseline characteristics were summarized by presenting counts and percentages. Visual inspection was used for assessment of normality of data distributions. Continuous, normally distributed variables were summarized by presenting the means and standard deviations. Continuous, non-normally distributed and ordinal variables were summarized by presenting the medians and interquartile ranges. Formal statistical tests were not performed to examine baseline differences between treatment groups. No bootstrapping was used for presentation of the baseline characteristics.

Table SAP1. Baseline characteristics

	CLI-RCT (n)	DBS-RCT (n)	CLI- observational (n)	DBS- observational (n)
Age (years)				
Sex, F (% n/N)				
Time since PD diagnosis (years)				
Hoehn and Yahr stage in on-drug state				
Levodopa-equivalent daily dose (mg/day)				
MDS-UPDRS part III score			NA	NA
- off-drug state				
- on-drug state				
- improvement off- to on-phase (%)*				
Parkinson's disease cognitive rating score			NA	NA
Level of experience of treating center with CLI and DBS treatment (%)**				
- Experienced in CLI, not in DBS				
- Experienced in DBS, not in CLI				
- Experienced in both CLI and DBS				
- Little experience in both CLI and DBS				

CLI: continuous intrajejunal levodopa infusion, DBS: deep brain stimulation, F: female, MDS-UPDRS: Movement Disorder Society's Unified Parkinson's Disease Rating Scale, mg: milligrams, NA: not available, RCT: randomized controlled trial

** Improvement: (score in off-drug state minus score in on-drug state) divided by score in off-drug state*

***Experienced in DBS/CLI: ≥ 5 patients treated per year in the two years previous to including the patient with the respective treatment in the treating center. A center may have changed in level of experience over time.*

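### The ancillary pooled regression picks baseline covariates by undefined 'significant' imbalance, which can leave confounders of a self-selected treatment unadjusted; a fixed covariate list is better and costs almost nothing.

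*SAP*

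**What the plan says.** Under *Ancillary patient preference observational study arms*, the SAP plans a multivariable regression of the change in PDQ-39 at 12 months in the mITT randomised patients and the preference patients together. The stated aim is more power to assess the impact of treatment. The model is described as "taking into account significant imbalanced baseline variables and participation in the RCT or preference observational study". No covariate is named, and no treatment-by-participation term is mentioned.

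Protocol section 8.8 describes a similar pooled regression, for follow-up PDQ-39 scores, but adjusts for *relevant* rather than *significant* imbalances. Neither word is defined. Under *Baseline characteristics*, in a section that covers both the RCT and the preference population, the SAP states: "Formal statistical tests were not performed to examine baseline differences between treatment groups".

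The same ancillary section also plans two comparisons on PDQ-39 change, each with a 95% CI: randomised v preference patients on CLI, and randomised v preference patients on DBS. The main clinical analysis is the RCT mITT t-test (SAP, *Analyses*).

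**The concern.** In the preference arms patients choose their treatment, so baseline differences between CLI and DBS patients reflect selection. Whether a variable confounds depends on its imbalance and its relation to outcome, not on whether the imbalance reaches significance in groups of this size. A rule based on significance tends to drop moderate imbalances in small groups.

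The rule also cannot be carried out as written. There is no threshold, and the SAP does not say which contrast is meant: CLI v DBS within the preference cohort, CLI v DBS in the pooled sample, or randomised v preference. The supplementary table SAP1-S gives intervals only for all randomised patients against each preference arm, so the CLI v DBS contrast that matters for confounding has no interval there. That table also omits baseline PDQ-39.

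Baseline PDQ-39 deserves a fixed place. The SAP (*Synopsis of study protocol development*) argues that a change score is largely independent of baseline differences. In self-selected groups that fails when the baseline-to-follow-up correlation is below 1.

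The participation main effect removes a difference in level between cohorts. It does not remove confounded treatment choice within the preference cohort, and it does not show whether the treatment effect differs between cohorts. At stake is how an ancillary but more precise-looking estimate is read beside a small RCT. Protocol section 12.6 says that preference-group analyses gain interest if the RCT's efficiency results are indecisive.

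**Working it through.** **Inputs.** RCT: "Accounting for a possible dropout of 20%, we will randomize 66 patients (33 per group"). Preference cohort (protocol 4.4): 108 DBS v 72 CLI as the main case; 120 patients as the low case, or 72 v 48 at the same 60/40 split. PDQ-39: "assuming an expected mean score of 32 in the DBS group and a standard deviation of 15". No SD for the change score is given, so 15 is assumed for it. No baseline-to-12-month correlation is given, so 0.5 to 0.7 is assumed.

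**The plan's own figures.** With SD 15, 80% power and two-sided 0.05, a noncentral-t calculation gives detectable differences of 11.89 (26 v 26), 8.42 (33 v 108), 8.92 (33 v 72) and 9.62 (33 v 48). Protocol 4.4 states 11.9, 8.4, 8.9 and 9.6, so the inputs are read correctly. No figure is stated for the pooled regression.

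**Share of non-randomised information.** In a model with treatment and cohort main effects, each cohort contributes information w = n1 × n2 / (n1 + n2), whatever the SD.
- RCT: 33 × 33 / 66 = 16.5
- Preference, 108 v 72: 43.2; share 43.2 / 59.7 = 72%
- Preference, 72 v 48: 28.8; share 28.8 / 45.3 = 64%

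Equal proportional loss in both cohorts leaves these shares essentially unchanged. Taking 20% dropout off the RCT only (26 per arm, w = 13) gives 69-77%. Taking it off the preference arms only gives 58-68%.

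**Would a 5-point baseline PDQ-39 imbalance be adjusted for?** This reads *significant* as P < 0.05 for CLI v DBS within the preference cohort.
- 72 v 48: SE = 15 × √(1/72 + 1/48) = 2.80; 5 / 2.80 = 1.79; P about 0.08; left out
- 108 v 72: SE = 15 × √(1/108 + 1/72) = 2.28; 5 / 2.28 = 2.19; P about 0.03; adjusted for

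**Bias if left out (72 v 48).** With equal SDs at both times, a baseline difference d shifts the change score by d × (1 − r), and the pooled estimate by that amount times the preference share.
- r = 0.5: 5 × 0.5 × 0.636 = 1.6 points
- r = 0.7: 5 × 0.3 × 0.636 = 1.0 point

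**Several moderate confounders.** A simulation of 3,000 trials (33 v 33 randomised, 108 v 72 preference) assumed no treatment effect and four confounders, each 0.3 SD apart between preference arms and each with a coefficient of 0.25 SD. Screening at P < 0.05 left a bias of 1.4 points and a type I error of 10.5%. Adjusting for all four gave 0 and 4.6%. These strengths of confounding are assumptions, not estimates.

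**Interaction.** SE = 15 × √(1/16.5 + 1/43.2) = 4.34, or 15 × √(1/16.5 + 1/28.8) = 4.63. Power for a 5-point interaction is 21% and 19% (17% with 26 per RCT arm and 72 v 48). On the normal approximation the RCT alone (33 per arm) detects 10.3 points and the pooled main-effects model 5.4 to 6.2. Most of the gain in power therefore rests on assuming equal treatment effects in both cohorts.

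**The case against.** Much of the case for leaving the plan alone is fair. The regression sits in the ancillary section, the main publication uses the RCT mITT population, only the main clinical outcome has a P-value rule, and the economic analyses use mITT. The preference arms serve primarily to examine external validity. The two randomised v preference contrasts are already reported with intervals, and their difference is an unadjusted treatment-by-participation interaction. What is missing is narrower: an adjusted interaction, a preference-only CLI v DBS effect with its interval, and a named covariate set. P < 0.05 is also a reading of *significant*, not a stated rule.

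Three stronger inferences are tempting and are not supported.
- *The pooled result could outweigh or stand in for the randomised estimate.* Nothing in the plan gives it that role.
- *The bias exceeds the SAP's 1.6-point minimal clinically important difference.* At 72 v 48 with 33 per RCT arm it is 1.59 even at a correlation of 0.5. It passes 1.6 in this example only if dropout is deducted from the RCT alone, and the correlation is in neither document. In the main planning case the same imbalance would be adjusted for.
- *The preference population and its imputation need changing because patients must have* "underwent at least the baseline visit and one follow-up visit". The documents give no count of patients this removes, so no effect on the pooled estimate can be shown.

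**Conclusion.** The concern holds as a cheap improvement to an ancillary analysis. The covariate rule is undefined, differs between protocol and SAP, sits badly with the no-testing statement, and is a poor way to control confounding where treatment is chosen. At planned numbers about 64-72% of the pooled treatment information would be non-randomised; the SAP sets no minimum for the preference arms and gives no actual count. The illustrated bias of about 1.0 to 1.6 PDQ-39 points depends on a 5-point imbalance at 72 v 48, a 0.05 cut-off, SD 15 and a correlation of 0.5 to 0.7. It shows that the rule can fail, not that it has failed. The primary RCT result is unaffected.

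**What to change.** Replace the phrase on significantly imbalanced variables with a fixed list, used whatever the P-values: baseline PDQ-39, age, time since diagnosis, Hoehn and Yahr stage, LEDD and centre experience. All are planned for both cohorts (protocol 7.3; SAP Tables SAP1, SAP2 and SAP4).

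Report the adjusted treatment-by-participation interaction as an estimate with a 95% CI. Do not use it as a gate for pooling: at 17-21% power for 5 points, a non-significant result would say little. Show the RCT-only, preference-only and pooled CLI v DBS effects side by side, and label the pooled estimate observational and exploratory.

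The cost is SAP wording and one small table, with no new data. The pooled interval may change slightly. Residual confounding remains, because Table SAP1 marks MDS-UPDRS part III and PD-CRS as not available in the preference arms; the report should say so.
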